### **3.3.1.2 Main analytical approach**

**3.3.1.2.1** *Number of weeks with platelet count  $\geq 50,000/\mu\text{L}$  OR between  $\geq 30,000/\mu\text{L}$  and  $< 50,000/\mu\text{L}$  and at least doubled from baseline over the 24-week blinded treatment period in the absence of rescue therapy;*

*Number of weeks with platelet counts  $\geq 30,000/\mu\text{L}$  and at least doubled from baseline over the 24-week Blinded Treatment period in the absence of rescue therapy*

The analysis of this key secondary endpoint is to compare the number of weeks with platelet response between the rilzabrutinib treatment group and the placebo treatment group via the primary estimand as defined in [Table 2](#).

Considering a participant's platelet response at each visit a binary response data, a mixed-effect model with repeated measures (MMRM) approach will be used to analyze the longitudinal binary platelet response data across visits (4) in the adult ITT population. The analysis model will include treatment, randomization stratification factors ([Section 3.1](#)), week (Weeks 2 to 25), treatment-by-week interaction as categorical fix effects. Generalized estimating equations will be used to obtain statistical inference. A variance component working covariance matrix which is merely a weight matrix will be used in the model to obtain unweighted proportions.

To prepare the data for MMRM analysis, each participant will have complete weekly response status across 24 weeks as a 24-dimensional vector after the handling of intercurrent events and missing data (specified below).

Least squares (LS) mean number of weeks (% weeks) with platelet response across 24 weeks in each treatment group, difference in LS mean number of weeks (% weeks) with platelet response between treatment groups and its corresponding 95% CIs will be provided along with the p-value.

For each of the adult and pediatric populations respectively, descriptive statistics (eg, mean, standard deviation, median, Q1, Q3, minimum and maximum) will be provided by treatment group for the number of weeks with observed platelet response.

**Intercurrent events** will be handled with the primary estimand as specified in [Table 2](#). Specifically,

1. Rescue medication: platelet counts will be censored for 4 weeks after the use of rescue therapy. That is, the weeks from the date when the rescue medication is initiated up to 4 weeks after the use of rescue medication, i.e. any weeks that fall into this period will be considered as not qualifying for the criteria specified, thus will be considered to have had no platelet response (hypothetical strategy).
2. Discontinuation of study intervention before Week 25: data during the double-blind on-treatment period will be included in the analysis. Post-treatment data will be considered to have had no platelet response (composite strategy).

**Missing data** (ie, missing weekly platelet counts) will be considered as no response.

**3.3.1.2.2 Time to first platelet count of  $\geq 50,000/\mu\text{L}$  OR between  $\geq 30,000/\mu\text{L}$  and  $< 50,000/\mu\text{L}$  and doubled from baseline during the 24-week Blinded Treatment period (platelet counts will be censored for 4 weeks after the use of rescue therapy, if any)**

The analysis of this key secondary endpoint is to compare the time to first platelet response as defined between the rilzabrutinib treatment group and the placebo treatment group via the primary estimand as defined in [Table 2](#).

To reject the null hypothesis of no treatment difference, the two-sided p-value based on a stratified log-rank test adjusted by randomization stratification factors ([Section 3.1](#)) must be  $< 0.05$  in the adult ITT population. The hazard ratio between rilzabrutinib and placebo along with its 95% confidence interval will be estimated based on a Cox regression model with treatment group and randomization stratification factors ([Section 3.1](#)) as covariates.

For each of adult and pediatric populations respectively, the K-M method will be used to estimate the probabilities of first platelet response in each group, along with 1st, 2nd (median) and 3rd quartile time to response. K-M plot will also be provided.

**Intercurrent events** will be handled with the primary estimand as specified in [Table 2](#). Specifically,

1. Rescue medication: platelet counts will be censored for 4 weeks after the use of rescue therapy. That is, the weeks from the date when the rescue medication is initiated up to 4 weeks after the use of rescue medication, i.e. any weeks that fall into this period will be considered as not qualifying for the criteria specified, thus will be considered to have had no platelet response (hypothetical strategy).

2. Discontinuation of study intervention before Week 25: data during the double-blind on-treatment period will be included in the analysis. Post-treatment data will be considered to have had no platelet response (composite strategy).

**Missing data** (ie, missing weekly platelet counts) will be considered as no response.

Participants who have never experienced platelet response (as defined in [Section 3.3.1.1](#)) any time during the 24-week double-blind treatment period will be censored,

- At 1 week after the protocol scheduled Week 25 (Day 169) visit for those who prematurely discontinued the 24-week treatment period due to related AE or lack of response, or,
- At the last assessment during the double-blind on-treatment period otherwise.

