Secondary endpoint (Hypothetical + composite estimand)	Time to first platelet count of $\geq 50,000/\mu\text{L}$ OR $30,000/\mu\text{L}$ to $< 50,000/\mu\text{L}$ and doubled from baseline in the absence of rescue therapy	ITT	
1) Rescue medication: platelet counts will be censored for 4 weeks after the use of rescue therapy. That is, the weeks from the date when the rescue medication is initiated up to 4 weeks after the use of rescue medication will be considered to have had no platelet response (hypothetical strategy).
 
2) Discontinuation of study intervention before Week 25: data during the double-blind on-treatment period will be included in the analysis. Post-treatment data will be considered to have had no platelet response (composite strategy).
	
Adults: p-value from stratified log-rank test adjusted by randomization stratification factors d. Hazard ratio and 95% CI from Cox regression model with treatment group and randomization stratification factors d as covariates.
 
Pediatrics: Descriptive.
 
Missing data will be considered as no response. If no platelet measurement is available at the weekly visit, that week will be considered to have had no platelet response.
 
Participants who never responded will be censored at 1 week after Week 25 if prematurely discontinued due to related AE or lack of efficacy; Otherwise censored at the last platelet count assessment during the double-blind on-treatment period.

Endpoint Category (estimand)	Estimands			
	Endpoint a	Population	Intercurrent event(s) handling strategy	Population-level summary (Analysis and missing data handling)

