#### **3.3.1.2.3 Proportion of participants requiring rescue therapy during the 24-week Blinded Treatment period**

The analysis of this key secondary endpoint is to compare proportion of participants requiring rescue therapy (via the time to event analysis due to the expected high rate of treatment discontinuation) during the 24-week blinded treatment period between the rilzabrutinib treatment group and the placebo treatment group via the primary estimand as defined in [Table 2](#).

To reject the null hypothesis of no treatment difference, the two-sided p-value based on a stratified log-rank test adjusted by randomization stratification factors ([Section 3.1](#)) must be  $<0.05$  in the adult ITT population. The hazard ratio between rilzabrutinib and placebo along with its 95% confidence interval will be estimated based on a Cox regression model with treatment group and randomization stratification factors ([Section 3.1](#)) as covariates.

For each of adult and pediatric populations respectively, the K-M method will be used to estimate the probabilities of first rescue therapy use at specific timepoints (eg, Weeks 9, 25) in each group, along with 1st, 2nd (median) and 3rd quartile time to first rescue therapy use. K-M plot will also be provided.

**Intercurrent events** will be handled with while-on treatment strategy, that is, rescue therapy during the double-blind period, ie, after first double-blinded IMP administration and before Week 25 (or last double-blinded IMP administration, whichever earlier), will be included in the analysis.

Participants who have not been rescued any time during the 24-week double-blind treatment period will be censored at Week 25 (Day 169) visit (or last double-blinded IMP administration, whichever earlier).

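### Time to first platelet response: the censoring rule for never-responders who stop for other reasons is hypothetical, but the stated estimand for discontinuation is composite

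*SAP*

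**What the plan says.** SAP Table 2 and Section 3.3.1.2.2 define the estimand and analysis for time to first platelet response, a key secondary endpoint in the fixed testing sequence of Section 3.5.

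- **Discontinuation before Week 25.** There is one rule for all reasons. On-treatment data are used, and "Post-treatment data will be considered to have had no platelet response (composite strategy" is how the rest is handled. Missing weekly counts are also treated as no response.
- **Censoring of never-responders, first branch.** Censoring falls "At 1 week after the protocol scheduled Week 25 (Day 169) visit for those who prematurely discontinued the 24-week treatment period due to related AE"; stopping because of insufficient response is handled alike.
- **Censoring of never-responders, second branch.** In Section 3.3.1.2.2: "At the last assessment during the double-blind on-treatment period otherwise". In Table 2: "Otherwise censored at the last platelet count assessment during the double-blind on-treatment period".
- **Analysis.** The test is "the two-sided p-value based on a stratified log-rank test adjusted by randomization stratification factors", with a hazard ratio from a Cox model. For description, "the K-M method will be used to estimate the probabilities of first platelet response in each group", with quartiles.

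The two number-of-weeks key secondaries (Section 3.3.1.2.1) carry the same discontinuation wording, and there "each participant will have complete weekly response status across 24 weeks as a 24-dimensional vector" is built before modelling.

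**The concern.** Under a composite strategy, a participant who stops without having responded is a non-responder for the rest of the period and must stay in the risk set to its end. The first censoring branch does this. The second removes a never-responder who withdraws, is lost to follow-up or stops for an unrelated adverse event at the last count. That treats stopping as non-informative, as if the participant would have gone on to respond at the rate of those still on treatment. The later weeks cannot be both no response and unobserved.

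The same participant is therefore a non-responder in every later week for the two number-of-weeks endpoints, and censored here. The reported response probabilities and quartiles would not estimate the stated estimand, and part of the result would depend on which discontinuation reason the site records.

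**Working it through.** **Could other text resolve it?**

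- For the rescue-therapy endpoint (Section 3.3.1.2.3), censoring at last dose is labelled while on-treatment.
- For ITP-PAQ Item 10 (Section 3.3.1.2.4), discontinuation is split by reason and the other-reason branch is labelled hypothetical.
- For the primary endpoint (Section 3.2.2), post-treatment data after other-reason discontinuation count as no response, labelled composite.
- The supplementary analysis in Section 3.3.1.3.1 keeps the primary-estimand handling for discontinuation not due to a related adverse event, so it does not test the point.

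Elsewhere the label matches the rule. For time to first response it does not.

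**Stated figures.** The documents give no response rate, event count or power for this endpoint. The only stated power, 95% for the primary endpoint (SAP Section 4; 129 vs 65 adults, 25% vs 5%, two-sided 0.05), comes out at 96.4% by exact enumeration of Fisher's test. I use the arm sizes 129 and 65 below.

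**Direction.** Suppose r participants are still on treatment without response, k have already left without response, and e respond at the next visit. The SAP rule multiplies the survival estimate by 1 − e/r; the composite rule multiplies it by 1 − e/(r + k). With k > 0 and e > 0 the first is smaller, so the SAP-rule response probability is never below the composite one, and is strictly above it once any response follows such a departure.

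**Hand example (assumed data).** Responders at Weeks 2, 4, 6, 8, 10 and 12: rilzabrutinib 25, 20, 12, 8, 6, 6 (77 of 129); placebo 6, 5, 4, 3, 2, 2 (22 of 65). About 10% leave at Week 5 for other reasons without response (13 and 6).

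- Rilzabrutinib, composite: 77/129 = 59.7%.
- Rilzabrutinib, SAP rule: 129 − 45 = 84 remain after Week 4, 84 − 13 = 71 after the departures, and 71 − 32 = 39 never respond. 1 − (84/129)(39/71) = 64.2%.
- Placebo, composite: 22/65 = 33.8%.
- Placebo, SAP rule: 1 − (54/65)(37/48) = 36.0%.

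With 5% to 20% leaving at a single week (3, 5 or 9), the SAP rule gives 60.7% to 73.1% on rilzabrutinib and 34.3% to 40.8% on placebo. These are large because every leaver is a never-responder and all leave together.

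**Spread-out dropout (assumed).** Let p be the proportion responding by 12 weeks, at a constant weekly hazard h = 1 − (1 − p)^(1/12). Let q be the chance of leaving for other reasons within 12 weeks if not yet responded, uniform over time. The Kaplan-Meier estimate targets p. The composite incidence is lower by

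q × m, where m = [1 − (1 − p)(1 + 12h)]/(12h).

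- Rilzabrutinib, p = 65%: h = 0.0838, m = 0.2966.
- Placebo, p = 33%: h = 0.0328, m = 0.1679.

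| q | Rilzabrutinib excess | Placebo excess |
|---|---|---|
| 5% | 1.5 points | 0.8 points |
| 10% | 3.0 points | 1.7 points |
| 15% | 4.4 points | 2.5 points |

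One standard error of the rilzabrutinib proportion is √(0.65 × 0.35/129) = 4.2 points. With front-loaded response the rilzabrutinib excess is 1.1, 2.2 and 3.3 points.

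**Test and hazard ratio.** Simulation with 1,500 trials per scenario, unstratified, weekly response hazard 8% vs 4%:

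| Other-reason dropout per week (rilzabrutinib vs placebo) | HR, SAP rule | HR, composite | Power, SAP rule | Power, composite |
|---|---|---|---|---|
| 2% vs 2% | 2.01 | 1.98 | 88% | 87% |
| 4% vs 1% | 2.04 | 1.69 | 88% | 63% |
| 1% vs 4% | 2.02 | 2.35 | 85% | 96% |

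**The case against.** The affected group is narrow. A participant who responded before stopping is an event under either rule, so one might infer that every discontinuation counts as non-response, but the SAP says this only of post-treatment data. The Week 13 gate (protocol Section 4) uses essentially the same platelet criterion as this endpoint. Those who continue blinded treatment have, deviations aside, already had the event, and few or no events follow the exit of the non-responders. Whether those Week 13 exits are censored then or after Week 25 therefore hardly moves the curve. That leaves never-responders who stop before about Week 13 for other reasons.

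A reader might size that group from Section 3.3.1.2.3, which chooses a time-to-event analysis "due to the expected high rate of treatment discontinuation". The documents do not support this: no figure is given, there is no split by reason, and nothing separates it from the planned Week 13 exits.

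The confirmatory result is the log-rank test, and the Kaplan-Meier figures are descriptive. Section 3.2.3.2 expects high dropout particularly on placebo. If that also held for other-reason dropout, the SAP rule would be conservative for the test. The adverse scenario needs 4% per week on rilzabrutinib, 1 − 0.96^12 = 39% over 12 weeks, which no document supports. Splitting by recorded reason is also not peculiar to this endpoint.

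Finally, the rule is explicit, prespecified and the same in both places. Under a hypothetical estimand with independent censoring it would be appropriate, so relabelling would also remove the contradiction.

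All of this stands as a limit on reach and size. None of it reconciles the composite label with the second censoring branch.

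**Conclusion.** As written, the censoring rule does not estimate the composite estimand that the SAP states for this endpoint. Relative to that estimand, the Kaplan-Meier response probability is biased upward in both arms whenever a response follows an other-reason discontinuation without prior response, mainly before Week 13. Under the spread-out assumptions the excess is about 1.5 to 4.4 points on rilzabrutinib and 0.8 to 2.5 on placebo for 5% to 15% dropout. The direction follows from the algebra; the size rests on assumed response and dropout rates.

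A reader might infer that the key secondary test is biased in favour of rilzabrutinib. The documents do not support that: the effect on the test and hazard ratio is negligible with balanced dropout, and with imbalance it can go either way. Nor is the Kaplan-Meier estimate wrong under every estimand. It is wrong for the one stated.

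**What to change.** In Table 2 and Section 3.3.1.2.2, censor every never-responder who discontinues before Week 25, for any reason, at 1 week after the scheduled Week 25 visit. Keep censoring at the last on-treatment assessment as a supplementary analysis. Never-responders who complete 24 weeks can stay as they are; censoring them at about Day 169 does no harm.

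If the sponsor prefers the current rule, label other-reason discontinuation as hypothetical in both places and add the composite version as a sensitivity analysis.

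The first option costs one sentence in two places and one derivation line; the reported response probabilities become slightly lower. The second costs similar wording changes and one additional run.

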#### **3.3.1.2.3 Proportion of participants requiring rescue therapy during the 24-week Blinded Treatment period**

The analysis of this key secondary endpoint is to compare proportion of participants requiring rescue therapy (via the time to event analysis due to the expected high rate of treatment discontinuation) during the 24-week blinded treatment period between the rilzabrutinib treatment group and the placebo treatment group via the primary estimand as defined in [Table 2](#).

To reject the null hypothesis of no treatment difference, the two-sided p-value based on a stratified log-rank test adjusted by randomization stratification factors ([Section 3.1](#)) must be  $<0.05$  in the adult ITT population. The hazard ratio between rilzabrutinib and placebo along with its 95% confidence interval will be estimated based on a Cox regression model with treatment group and randomization stratification factors ([Section 3.1](#)) as covariates.

For each of adult and pediatric populations respectively, the K-M method will be used to estimate the probabilities of first rescue therapy use at specific timepoints (eg, Weeks 9, 25) in each group, along with 1st, 2nd (median) and 3rd quartile time to first rescue therapy use. K-M plot will also be provided.

**Intercurrent events** will be handled with while-on treatment strategy, that is, rescue therapy during the double-blind period, ie, after first double-blinded IMP administration and before Week 25 (or last double-blinded IMP administration, whichever earlier), will be included in the analysis.

Participants who have not been rescued any time during the 24-week double-blind treatment period will be censored at Week 25 (Day 169) visit (or last double-blinded IMP administration, whichever earlier).

#### **3.3.1.2.4 Change from baseline on Item 10 of the ITP-PAQ (ie, physical fatigue) in adult participants ( $\geq 18$ years) at Week 13**

The analysis of this key secondary endpoint is to compare the change from baseline at Week 13 on Item 10 score of ITP-PAQ ([Section 3.7.3.2](#)) between the rilzabrutinib treatment group and the placebo treatment group in the adult ITT population via the primary estimand as defined in [Table 2](#).

Change from baseline in Item 10 score at Week 13 will be analyzed using an analysis of covariance (ANCOVA) model with the treatment group, randomization stratification factors and geographic region ([Section 3.1](#)) as fixed effects and baseline Item 10 score as a covariate. Missing score at Week 13 will be imputed via worst observation carried forward (WOCF) or multiple imputation as specified below which will result in multiple data sets of complete data. Each complete dataset will be analyzed by fitting an ANCOVA model. Statistical inference obtained from all imputed data will be combined using Rubin's rule (3). LS mean score changes in each treatment group, LS mean difference between treatment groups and their corresponding 95% CIs will be provided along with the p-value.

Observed Item 10 score at each visit and its change from baseline will be descriptively summarized. Cumulative distribution functions of Item 10 score in changes from baseline to Week 13 will be displayed by treatment groups. A shift summary from baseline to Week 13 and Week 25 will be provided for Item 10 raw score categorically.

**Intercurrent events** will be handled with a hybrid of composite and hypothetical strategy ([Table 2](#)). Specifically,

1. Rescue medication (after the initial 8 weeks of double-blind treatment): data after initiation of rescue therapy will be imputed by the participant's worst post-baseline value on or before the use of rescue therapy, ie, worst observation carried forward (for participants whose post-baseline values are all missing, the baseline value will be used to impute the missing Week 13 value) (composite strategy). For the purpose of worst observation carried forward, data will be set to missing for 4 weeks after the use of rescue therapy. In other words, only data more than 4 weeks after the use of rescue therapy will be carried forward.
2. Discontinuation of study intervention before Week 13 due to lack of response or related adverse events: the same handling as 1) above (composite strategy).
3. Discontinuation of study intervention before Week 13 due to reasons other than the aforementioned: data at Week 13 during the double-blind on-treatment period will be included in the analysis. Post-treatment data will be considered missing (hypothetical strategy).

Note, per protocol the end of study visit is performed at 4-week post-dose follow up where participants will have their final assessment.

**Missing data** will be handled as followed,

- A multiple imputation approach will be used to impute missing Week 13 value, using all data during the double-blind on-treatment period up to Week 13 from participants who did not take rescue medication (after 8 weeks of double-blind treatment), nor discontinued before Week 13 due to related AE or lack of response, assuming missing at random and multivariate normal distribution. The imputation model will include treatment group, randomization stratification factors, geographic region ([Section 3.1](#)) as classified variables and baseline item score as a covariate. In case the baseline score is missing for a participant, the pooled mean of baseline score will be used.

Note: before multiple imputation, data will be set to missing for 4 weeks after the use of rescue therapy.

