Appendix 10.7 EU (EEA countries) and UK-specific requirements

Synopsis, Section 3.1 Objectives, Section 3.1.1 Efficacy Objectives, Section 3.2 Endpoints, Section 10.3.9 Primary Efficacy Analysis; In the UK and countries within the EU (EEA countries):

- The primary endpoint in the blinded treatment period is the proportion of participants able to achieve platelet counts at or above 50,000/ μ L for at least 8 out of the last 12 weeks of the 24-week blinded treatment period in the absence of rescue therapy.
- The primary efficacy analysis is as follows: The primary analysis will compare the proportion of participants in the adult ITT population who achieve durable platelet response defined as platelet counts at or above 50,000/ μ L for ≥ 8 out of the 12 scheduled observations in the last 12 weeks of the 24-week blinded treatment period in the absence of rescue medication between rilzabrutinib and placebo with a Cochran-Mantel-Haenszel test using the two stratification factors at a 2-sided alpha level of 0.05. Participants who do not respond in the first 12 weeks and enter the open label period will be treated as non-responders in the primary analysis. Participants who discontinue the study due to a rilzabrutinib-related AE, lack of efficacy or receive rescue medication (including an increase in allowed concomitant ITP medications dose) will be considered as non-responders. Sensitivity analyses will be conducted on the primary analysis.
- In the blinded treatment period, the following is a key secondary objective: To evaluate the change from baseline in IBLS.

- In the blinded treatment period, the following is a key secondary efficacy endpoint (the last endpoint in the multiplicity control): Change from baseline in IBLS assessment at Week 25
- Key secondary efficacy analysis: Compare the change from baseline in IBLS assessment at Week 25

EU (EEA countries) only

Throughout the protocol, the allowed age range for pediatric participants is ≥ 10 to < 18 years, where permitted by local regulation.

Synopsis and Section 5.1, Inclusion criterion 1:

Participants will be male and female with primary ITP with duration of > 6 months in pediatric participants aged ≥ 10 to < 18 years (where allowed by local regulation) and duration of > 3 months in adults ≥ 18 years.

Synopsis and Section 5.1, Inclusion criterion 3:

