### 1.2.2.2 Key Secondary Efficacy Endpoints (Blinded Treatment Period)

- Number of weeks with platelet count  $\geq$ 50,000/ $\mu$ L OR between  $\geq$ 30,000/ $\mu$ L and  $<$ 50,000/ $\mu$ L and at least doubled from baseline over the 24-week blinded treatment period in the absence of rescue therapy.
- Number of weeks with platelet counts  $\geq$ 30,000/ $\mu$ L and at least doubled from baseline over the 24-week blinded treatment period in the absence of rescue therapy.
- Time to first platelet count of  $\geq$ 50,000/ $\mu$ L OR between  $\geq$ 30,000/ $\mu$ L and  $<$ 50,000/ $\mu$ L and doubled from baseline.
- Proportion of participants requiring rescue therapy during the 24-week blinded treatment period.
- Change from baseline on Item 10 of the ITP-PAQ (ie, physical fatigue) in adult participants ( $\geq$ 18 years) at Week 13.
- Change from baseline in IBLS assessment at Week 25 (applicable to countries within the EU (EEA countries) and UK only).

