Secondary endpoint (Composite + hypothetical estimand)	Change from baseline in physical fatigue (Item 10 of the ITP-PAQ) in adults at Week 13 b	ITT	1) Rescue therapy (after 8 weeks of double-blind treatment): data after the initiation of rescue therapy will be imputed by the participant's worst post-baseline value on or before the use of rescue therapy, ie, worst observation carried forward, (for participants whose post-baseline values are all missing, the baseline value will be used to impute the missing Week 13 value) (composite strategy). 2) Discontinuation of study intervention before Week 13 due to lack of response or related adverse events: the same handling as 1) above (composite strategy). 3) Discontinuation of study intervention before Week 13 due to reasons other than the aforementioned: data during the double-blind on-treatment period up to Week 13 will be included in the analysis. Post-treatment data will be considered missing (hypothetical strategy).	Adults only: p-value, least squares mean difference and 95% CI from an analysis of covariance (ANCOVA) model with treatment group, randomization stratification factors d and geographic region as fixed effects, and baseline value as a covariate.  Missing data handling: A multiple imputation approach assuming missing at random will be used to impute missing Week 13 value, using all data during the double-blind on-treatment period up to Week 13 from participants who did not take rescue medication (after 8 weeks of double-blind treatment), nor discontinued before Week 13 due to related AE or lack of response. Note: before imputation (worst observation carried forward or multiple imputation), data will be set to missing for 4 weeks after the use of rescue therapy.

Endpoint Category (estimand)	Estimands			
	Endpoint a	Population	Intercurrent event(s) handling strategy	Population-level summary (Analysis and missing data handling)
Secondary endpoint (Composite + hypothetical estimand)	Change from baseline in IBLS assessment at Week 25 c	ITT	The same handling as for ITP-PAQ Item 10 above except that Week 25 will replace Week 13.	Adult population: p-value from ANCOVA with treatment group and randomization stratification factors d and geographic region as fixed effects and baseline value as a covariate.  Pediatrics: Descriptive.  The same handling of missing data as for ITP-PAQ Item 10 above except that Week 25 will replace Week 13.

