a Additional secondary/exploratory endpoints that are not included in this table will be handled with a similar strategy by the endpoint type (ie continuous, proportion, time-to-event) during respective periods (double-blind, open-label, long-term extension).

b Not applicable to countries within the EU (EEA countries) and UK.

c Applicable to countries within the EU (EEA countries) and UK only.

d Randomization stratification factors are splenectomy status (yes, no) and severity of thrombocytopenia (platelet counts <15,000/μL, ≥15,000/μL).

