Participants requiring rescued therapy are those who are rescued after first double-blinded IMP administration and before Week 25 or last double-blinded IMP administration, whichever earlier. The Kaplan-Meier (K-M) method will be used to estimate the probabilities of first rescue therapy use. Please see handling of intercurrent events and the censoring rule in [Section 3.3.1.2.3](#).

*Change from baseline in Item 10 of ITP-PAQ at Week 25; Change from baseline in IBLIS assessment at Week 13*

Please refer to [Section 3.7.3](#).

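### The carry-forward rule for the Item 10 fatigue key secondary contradicts itself, IBLS inherits it, and the place of Item 10 in the EU/UK test sequence is stated inconsistently.

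*SAP*

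**What the plan says.** **Carry-forward rule.** SAP 3.3.1.2.4, item 1, covers rescue after the first 8 weeks of blinded treatment. Data after rescue are "imputed by the participant's worst post-baseline value on or before the use of rescue therapy", with baseline as the fallback if every post-baseline value is missing. The item then sets data to missing for 4 weeks after rescue and closes with the statement that "only data more than 4 weeks after the use of rescue therapy will be carried forward". Item 2 gives discontinuation for lack of response or a related adverse event the same handling. SAP 3.3.1.2.5 applies the handling to IBLS, with Week 25 in place of Week 13.

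Table 2 has the "worst post-baseline value on or before the use of rescue therapy" rule and a note that data are set to missing for 4 weeks after rescue before any imputation. It does not restrict carry-forward to later data.

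**Regional scope.** Table 2 attaches footnote b to Item 10: "Not applicable to countries within the EU (EEA countries) and UK". SAP 1.2.1.2 and 1.2.2.2 list Item 10 with no regional limit and restrict only IBLS. Protocol Appendix 10.7 makes IBLS at Week 25 a "key secondary efficacy endpoint (the last endpoint in the multiplicity control" and does not mention Item 10. SAP 3.5 applies a fixed sequence at two-sided 5%, and its text gives no regional order.

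**Week.** SAP 3.3.1.1 has a line naming "Change from baseline in Item 10 of ITP-PAQ at Week 25" and IBLS at Week 13. SAP 1.2.2.2 lists "Change from baseline on Item 10 of the ITP-PAQ (ie, physical fatigue) in adult participants" at Week 13 and IBLS at Week 25.

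**The concern.** Both endpoints are in the alpha-controlled sequence, so the value assigned after rescue should follow from one rule. The composite strategy is meant to count rescue as an unfavourable outcome by holding the participant at the worst value seen before it. A rule that allows only values recorded well after rescue does something else: it leaves nothing to carry, or it credits the participant with scores obtained after rescue treatment. If two rules are in the text when adults are unblinded, whoever programs the analysis chooses between them, and a choice made after unblinding could be data-dependent.

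The regional inconsistency decides whether a failed Item 10 test blocks IBLS in the EU/UK. If Item 10 is in that sequence and misses 0.05, IBLS cannot be formally tested. If it is not, IBLS follows the rescue endpoint directly.

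**Working it through.** The plan gives no power, SD, effect size or rescue rate for Item 10, so there is no plan figure to reproduce. The check is day arithmetic and scoring.

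**Inputs**
- Post-baseline Item 10 visits up to Week 13: Weeks 5, 9 and 13, that is Days 29, 57 and 85 (SAP 5.7.4; Protocol Table 1).
- Rescue in scope: after 8 weeks, so Day 57 or later.
- Visit window for Week 13: ±3 days, to Day 88 (Protocol Table 1). Analysis window for an unscheduled value: to Day 85 + 14 = Day 99 (SAP Table 12).
- Item 10 scoring: 100 × (5 − raw)/4, so raw 1 to 5 gives 100, 75, 50, 25, 0 (SAP 3.7.3.2 and 5.5.3).

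**Item 10 at Week 13.** The first day more than 28 days after rescue is the rescue day + 29.

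| Rescue day | First eligible day | By Day 85? | By Day 88? | By Day 99? |
|---|---|---|---|---|
| 57 | 86 | no | yes | yes |
| 59 | 88 | no | yes | yes |
| 60 | 89 | no | no | yes |
| 70 | 99 | no | no | yes |
| 71 | 100 | no | no | no |

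The first rule draws on Week 5 and Week 9. The closing sentence can draw only on a late Week 13 value, and only for rescue on Days 57 to 59 (visit window) or Days 57 to 70 (unscheduled value). The two pools do not overlap.

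**Illustration, with assumed scores.** Raw baseline 3, Week 5 = 4, Week 9 = 2, Week 13 = 2, transformed to 50, 25, 75, 75.
- First rule: min(25, 75) − 50 = −25.
- Closing sentence, no eligible value, baseline used: 50 − 50 = 0.
- Closing sentence, rescue on Day 57 and Week 13 taken on Day 86: 75 − 50 = +25.

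The second line takes the baseline fallback by extension, since the SAP words it for participants with no post-baseline value at all.

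**IBLS at Week 25.** Take rescue on Day 100 in a participant who stays on blinded treatment (assumed). The first rule uses Days 29, 57 and 85. The closing sentence starts at Day 129 and so uses Days 141 and 169, all after rescue.

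**EU/UK sequence.** Suppose the endpoints through rescue therapy succeed, Item 10 has p > 0.05 and IBLS has p < 0.05. If footnote b governs the sequence, IBLS can be claimed. If SAP 1.2.2.2 and Appendix 10.7 govern, it cannot.

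**The case against.** The strongest reply is that the closing sentence is badly placed rather than wrong. The SAP version 2 change entry says worst value carried forward is applied after censoring for rescue, and the Table 2 note gives the same order. On that reading the sentence only removes values recorded within 4 weeks of an earlier rescue. With rescue on Day 20 and again on Day 65, Week 5 (Day 29, 9 days after the first) drops out and Week 9 (Day 57, 37 days after it) is carried. SAP 3.2.3.1.2 uses the same device and limits it expressly to rescue in the first 8 weeks. This is probably the intent. It does not repair the text: the sentence stands under rescue after 8 weeks, mentions no earlier rescue, and excludes everything else. The sample code in 5.7.4 does not settle it, because it starts from a dataset already carried forward.

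On the EU/UK order, SAP Figure 1 sets out the fixed sequence and may answer the question; it is not reproduced in the copy reviewed. Table 11 says Item 10 replaced IBLS outside the EU/UK, so footnote b may be deliberate. The inconsistency with SAP 1.2.1.2 and 1.2.2.2 remains either way.

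A reader might also infer from 3.3.1.1 that the confirmatory week is in doubt. The documents do not support that. The section sends the reader to 1.2.2.2 for definitions, 3.3.1.2.4 and 3.3.1.2.5 analyse Item 10 at Week 13 and IBLS at Week 25, and 3.3.1.4 makes the swapped versions supplementary.

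**Conclusion.** The carry-forward rule in 3.3.1.2.4 contradicts itself and Table 2, on an alpha-controlled endpoint and on a second one that inherits it. For Item 10 the literal sentence leaves essentially no eligible value up to Week 13. For IBLS at Week 25 it would carry post-rescue values. Footnote b also conflicts with SAP 1.2.1.2 and 1.2.2.2. How that affects the test sequence depends on Figure 1.

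The size is limited to the individual level. Where the rules give different Item 10 values, the gap is at least one level, 25 points, and its direction can go either way.

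Three stronger readings are not supported:
- That every participant rescued after Week 8 gets a different value. The readings coincide when, for example, the worst pre-rescue value equals baseline and the literal rule falls back to baseline.
- That the treatment difference shifts by a stated number of points. This needs the share of each arm that moves and the direction of each move, and the documents give neither. Participants who discontinue without ever being rescued should not be counted, because they have no rescue date for the sentence to act on.
- That Appendix 10.7 expressly keeps Item 10. It is silent. That Item 10 precedes IBLS in the EU/UK is an inference from that silence, the final position given to IBLS, and SAP 1.2.2.2.

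**What to change.** In SAP 3.3.1.2.4 item 1, delete the closing sentence and state one rule, for example: *values recorded within 4 weeks after any rescue are set to missing; the worst remaining post-baseline value recorded on or before the qualifying rescue (or, for discontinuation due to lack of response or related AE, on or before discontinuation) is carried to Week 13 (Week 25 for IBLS); if none, baseline.* Use the same wording in Table 2.

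Reconcile footnote b with Figure 1 and Protocol Appendix 10.7, and say in SAP 3.5 whether IBLS is tested after Item 10 in the EU/UK. As written, Appendix 10.7 and SAP 1.2.2.2 imply that it is.

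As an editorial correction, swap the weeks in 3.3.1.1 so that Item 10 is at Week 13 and IBLS at Week 25.

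The cost is SAP wording only, with no change to data collection or sample size. It should be done before the adult data are unblinded for the early analysis.
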